The study is proposed to last three years after initial vaccination for each participant. Once the last study visit is completed, the participant chart will be reviewed to ensure that all serious adverse events are resolved or, if chronic conditions are present, that they are under medical care. The participant will then be closed out from the study. As mentioned above, if the GMT for 1 dose at the group level is inferior to that of 3 doses based on the 36-month analysis, all 1-dose girls will be invited to receive the 2nd dose of an HPV vaccine. Previous trials documented that delayed administration of a booster dose did not diminish the subsequent increase in antibody levels (58).

ANALYSIS PLAN

Primary Analytical Cohort

To evaluate the non-inferiority objective in the trial, an According to Protocol (ATP) analytical cohort will be defined. The ATP cohort for a specified HPV type (i.e. HPV 16 or HPV 18) and timing (i.e. 24-month or 36-month) are the participants who satisfy the following set of requirements:

- Received the correct number of doses within the predefined ATP vaccination windows. Denoting T_1 as the time of the first vaccination, the analytical window for the second vaccination is between T_1+30 days and T_1+90 days. Denoting T_2 as the time of the second vaccination, the analytical window for the third vaccination is between T_2+90 days and T_1+360 days.
- Not seropositive at baseline for the specified HPV type.
- Blood collected within the predefined ATP follow-up windows.
- No HPV vaccination outside of the study prior to blood collection. The participant did not report receiving an HPV vaccine and, among those tested, did not have HPV6 and HPV11 vaccine-level antibodies.

The cutoff for HPV16 seropositivity is greater than 1.41 international units (IU)/mL and for HPV18 is greater than 1.05 IU/mL. All serological measurements will be presented in international units. Restricting to HPV16 or 18 seronegatives using this cutoff also aligns the Gardasil cohort in this study with the efficacy cohort used in the licensure of Gardasil (Future I and II) (12).

Immunogenicity Endpoint

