Because the national vaccination program has been initiated, there is the potential that some girls enrolled at ages 9-10 years may have received an additional vaccination dose but have failed to report it. Therefore, we plan to conduct the following secondary/sensitivity analysis. We will compare GMTs, distributions, and seroconversion rates for HPV-16 and HPV-18 antibodies, assessed at 24 and 36 months after initial vaccination, between 11-14 year old girls receiving 1 dose of Cervarix and 18-25 year old women receiving 3 doses of Gardasil. We will also calculate the GMT ratios, comparing girls 9-10 years old at vaccination with girls 11-14 years old at vaccination, and their 95% confidence intervals for HPV-16 and HPV-18 antibody levels at 1 month and 1-year post-vaccination. Additionally, we will test for HPV6/HPV11 antibodies in a subset of participants who are at-risk for external HPV vaccination or show serologic evidence of additional HPV vaccine doses.

Power and Sample Size Considerations

We calculate the power to show non-inferiority at 24 months and the power to show non-inferiority at 36 months given that we enroll 520 women 18-25 year old and 347 girls 9-14 year old. Specifically, we assume that $\hat{\sigma} = 1.38$, 20% of all 18-25 year old women do not receive all 3 doses, 100% of 9-10 year old girls (i.e. worst case scenario) receive a vaccination outside the study, 20% of all participants are lost-to-follow up, 10% of the 18-25 year old women are seropositive at baseline, 5% of the 11-14 year old girls are seropositive at baseline, the common true ratio, R, for HPV-16 and HPV-18 is 1, and the non-inferiority threshold (t) is 0.67, in accordance with the recommendation of the WHO Expert Committee on Biological Standardization(60). Based on these assumptions, we will have 65% power to demonstrate non-inferiority at 24 months and 84% power to demonstrate non-inferiority at 36 months. Power calculations for other values of R and t are listed in table 4. Note the power reported for 36 months is $\Pr(\min(\hat{R}_{0.02}^{16}(36), \hat{R}_{0.02}^{18}(36)) > t)$, a lower bound for the probability of rejecting non-inferiority at either the 24- or 36- month analysis. In the more optimistic scenario, where 9-10 year old participants do not receive vaccinations outside the study, our power increases to 78% at 24 months and 91% at 36 months.

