- Blood collected within the predefined follow-up window. Denoting T_1 as the time of the first vaccination, the window for the 24-month visit is between T_1+700 days and T_1+912 days and the window for the 36-month window is T_1+1065 days and T_1+1278 days.
- No HPV vaccination outside of the study prior to blood collection. The participant did not report receiving an HPV vaccine and, among those tested, did not have HPV6 and HPV11 vaccine-level antibodies.

Note, the ATP cohort for a given analysis depends on both the timing of the analysis and the specified HPV type.

3b. Secondary/Exploratory Analytical Cohorts

We will also consider the: (i) modified Intention-to-Treat (ITT) cohort, including all participants receiving the correct number of doses and with blood collected during the predefined follow-up window; (ii) Seropositive-ATP (SP-ATP) cohort that includes participants who are seropositive at baseline, but otherwise satisfy the ATP requirements; and (iii) Serocombined-ATP (SC-ATP) cohort that combines the ATP and SP-ATP cohorts. Furthermore, for SO4, we will consider all

girls who are not seropositive at baseline, had blood collected between $T_1 + 14$ and $T_1 + 90$ days for the 1 month analysis and between $T_1 + 274$ and $T_1 + 547$ days for the 1 year analysis, and did not receive an HPV vaccination outside of the study prior to their blood collection. Additionally, we will test for HPV6/HPV11 antibodies in a subset of participants who are at-risk for external HPV vaccination or show serologic evidence of additional HPV vaccine doses.

4. Endpoints

The four endpoints are HPV-16 and HPV-18 specific antibody results obtained from blood specimens (serum) collected at the 24- (interim) and 36-(primary) month visit (i.e. 4 endpoints = 2 HPV types x 2 time-points). All antibody levels are measured by HPV type-specific ELISA. Two additional endpoints, HPV-16 and HPV-18 antibody levels measured from serum collected at the 1-month visit and the 1-year visit, will also be included to achieve Secondary Objective 4 (SO4).

5. Implementation of Analysis

The final 24- and 36-months analyses will be performed once the corresponding follow-up window for the last enrolled participant closes

6. Controlling the Type-I error rate

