Secondary Objective 2 (SO2): For each combination of HPV-type, time-point, and study group, we will report the proportion of the ATP cohort who seroconvert (i.e. achieve HPV-16 or HPV-18 antibody levels greater than 1.41 international units (IU)/mL or 1.05 IU/mL, respectively) and exact 95% confidence intervals. For each HPV-type and time-point, we will assess whether seroconversion rates differ between study groups using fisher's exact test.

Secondary Objective 3 (SO3): We will repeat the analyses described for the primary objective and secondary objectives 1 and 2 restricted to 11-14-year-old girls. We will also perform a direct comparison of the antibody levels in 9-10 and 11-14 year old girls (e.g. compare GMT in GEE w/ age group as the independent variable, compare seroconversion rates by fisher's exact test).

Secondary Objective 4 (SO4): We will repeat the analyses described for the primary objective and secondary objectives 1 and 2 to compare antibody levels at 1-month and 1-year post-vaccination in girls 9-10 years old girls and in girls 11-14 years old.

Secondary Objective 5 (SO5): We will consider the following baseline covariates: age, enrollment date, and district. Within each study-group and at each time point, we will report the GMTs and their 95% CIs for HPV-16 and HPV-18 antibody levels in subgroups defined by these baseline covariates. Moreover, we will use GEEs to assesses the association between GMTs and these baseline covariates and show both reverse cumulative distributions and seroconversion rates by subgroup.

7c. Methods for Sensitivity and Exploratory Analyses

We will repeat the methods for the primary and secondary objectives using the ITT, SP-ATP, and SC-ATP cohorts instead of the ATP cohort.

We will repeat the methods for the primary and secondary objectives after removing potential outliers (e.g. participants potentially exposed to a vaccination outside of study) where the antibody level is $2 \times \text{IQR}$ above the 75th percentile.

We will assess whether antibody levels are changing over time. For each combination of study group and HPV type, we will compare GMTs at 24 and 36 months.

8. Statistical Analyses for Evaluating ELISA assays And Comparability with SEAP-NA

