HPV binding is measured by ELISA. The quantity of HPV16 and 18 IgG antibody response measured by VLP ELISA will be utilized to address immunogenicity endpoints. To further define the primary analytic cohort, HPV6 and HPV11 antibodies will be measured by VLP ELISA in a subset of participants to confirm, beyond self-report, that the according to protocol analytic cohort includes only girls who did not receive external HPV vaccination through the national program, which uses quadrivalent vaccine (HPV 6, 11, 16, 18). This will assure that girls in the single-dose HPV vaccination arm did not get additional doses.

HPV neutralization is measured by SEAP-NA. Antibodies levels measured by ELISA will be compared to neutralizing antibody levels measured by the pseudovirion-based neutralization assay, SEAP-NA. This nested study will select 24- month serum samples from a random set of 100 baseline seronegative 18-25 year old women and a random set of 100 baseline seronegative 9-14 year old girls, and then evaluate the HPV-16 and HPV-18 antibody levels in each of those 200 samples using both ELISA and SEAP-NA. For each HPV type, we will perform a Deming regression comparing $\log(\text{ELISA})$ levels with $\log(\text{SEAP})$ levels, where $\log(\text{ELISA})$ is the dependent variable and $\log(\text{SEAP})$ is the independent variable. We will confirm that ELISA is an acceptable assay for the primary endpoint if the 95% confidence intervals of the regression slope excludes $1-\Delta$ and $1+\Delta$ for both HPV types, with $\Delta = 0.3$. If that criterion is not achieved, then we will initiate a discussion with relevant parties to assess acceptability of the assay.

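### Does HPV6/11 testing of only a subset leave girls with unreported outside doses in the primary cohort?

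*SAP*

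**What the plan says.** SAP section 3a, and the protocol under Primary Analytical Cohort, remove outside vaccination from the ATP cohort by two routes. A girl qualifies if she "did not report receiving an HPV vaccine and, among those tested, did not have HPV6 and HPV11 vaccine-level antibodies". Self-report therefore applies to everyone and serology only to those tested.

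SAP section 3b, and the protocol under Analysis, describe who is tested: "a subset of participants who are at-risk for external HPV vaccination or show serologic evidence of additional HPV vaccine doses". Neither document defines the at-risk group, the serologic trigger, the visit whose serum is used or the vaccine-level cutoff.

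SAP section 8, and the protocol under Serology, then state the purpose: "This will assure that girls in the single-dose HPV vaccination arm did not get additional doses".

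The protocol's Analysis section says why this matters: "some girls enrolled at ages 9-10 years may have received an additional vaccination dose but have failed to report it". For that reason SAP section 7b (SO3) adds: "We will repeat the analyses described for the primary objective and secondary objectives 1 and 2 restricted to 11-14-year-old girls". SAP section 7c adds an analysis that removes high outliers.

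**The concern.** Testing a subset cannot assure anything about girls outside it, and the words "among those tested, did not have HPV6 and HPV11 vaccine-level antibodies" show that the plan expects untested girls. The protocol doubts self-report in just the group where it is the only check on an untested girl. That group is about a third of the single-dose arm (173 of 520).

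An extra dose raises the titre, so every missed dose moves the 1-dose GMT up and the ratio toward non-inferiority. That is the result meant to support a label change, and the trial is open-label. The visit questions are self-report again. Stopping enrolment of 9-10s does not reach those already enrolled. SO3 and the outlier analysis lie outside the primary decision rule. On this view the primary cohort has an open door that biases in one direction.

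**Working it through.** **1. Reproduce the protocol's power.** Inputs from Power and Sample Size Considerations: SD of log titre 1.38; 20% of women without all three doses; 20% loss; 10% of women and 5% of girls seropositive; margin 0.67; true ratio 1; one-sided levels 0.005 (24 months) and 0.02 (36 months).

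- Women: 520 × 0.8 × 0.8 × 0.9 = 299.5
- Girls 11-14: 347 × 0.8 × 0.95 = 263.7
- Girls 9-10: 173 × 0.8 × 0.95 = 131.5; all girls 395.2
- SE = 1.38 × √(1/n_women + 1/n_girls); power = [Φ(−ln 0.67/SE − z)]², the two types taken as independent

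With 263.7 girls, power is 64.9% and 84.0% (stated 65% and 84%). With 395.2 girls it is 78.7% and 91.9% (stated 78% and 91%).

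The stated worst case, "100% of 9-10 year old girls (i.e. worst case scenario) receive a vaccination outside the study", therefore drops all the 9-10s from the calculation. It does not describe contaminated girls left in the analysis.

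**2. Size of the bias if nobody is caught.** Assumptions, since the documents give no figures: a fraction p of all girls has a missed dose; each such dose multiplies the titre by k; the correlation between looks is 0.8. The range for k is 2 to 6.6. The upper value is the protocol's 3- versus 1-dose Cervarix ratio for HPV-16 at 36 months.

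- GMT shift = exp(p ln k) − 1
- SE = √(1.38²/299.5 + (1.38² + p(1−p)(ln k)²)/395.2); d = p ln k/SE
- False declaration with one type at exactly 0.67 and the other clear = 1 − Φ₂(2.576 − d, 2.054 − d; 0.8)

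| p | GMT shift | False declaration |
|---|---|---|
| 0 | 0 | 0.022 |
| 1% | 0.7% to 1.9% | 0.025 to 0.033 |
| 2% | 1.4% to 3.8% | 0.030 to 0.049 |

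At p = 2%, a look correlation of 0.5 gives 0.033 to 0.054 and 0.9 gives 0.028 to 0.046. With both types at 0.67 (type correlation 0.5 assumed), the error is 0.004 with none missed and 0.006 to 0.011 at 2%.

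**3. What p = 2% requires.** p = (173/520) × share of 9-10s vaccinated outside × share of those neither reporting nor tested. The last share must be 0.02 × 520/173 = 6% if all were vaccinated outside, 12% if half, and 24% if a quarter.

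**4. Allow for the serologic trigger.** The plan also tests girls with serologic evidence of extra doses. The plan gives no trigger, so take as an example the SAP section 7c outlier rule, upper quartile plus 2 × IQR on the titre scale. With SD 1.38 the threshold is 1.92 log units above the unboosted median. It flags 19% (k = 2) to 49% (k = 6.6) of boosted girls, who are then tested and removed. The residual shift is p(1−f)·E[x | x < 1.92]/(1−pf), where f is the flagged share. At p = 2% this is 0.4% to 0.8%, and the error is 0.024 to 0.026.

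**5. Does testing every 9-10 gain power?** No. The higher figures, "our power increases to 78% at 24 months and 91% at 36 months", apply when no 9-10 is vaccinated outside. The primary analysis already includes the 9-10s, so testing can only remove girls. With 25% of them excluded (362.3 girls), power is 76% and 91%. With 50% excluded (329.5 girls) it is 73% and 89%.

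**The case for a change.** The best case for a change is that the gap sits in the definition of the primary cohort, the bias has one direction, and closing it is cheap: at most 206 stored sera per visit (206 × 0.8 × 0.95 = 157 after expected losses) on an assay already planned. The size also depends on rules the plan leaves unstated. If the at-risk list left out many 9-10s, the bias would not be small: with 20% of them undetected and a 4-fold rise, the ratio is inflated by 4^(0.333 × 0.2) − 1 = 9.7%. SO3 cannot settle the matter afterwards either. With none missed and a true ratio of 1, a primary pass is followed by an SO3 failure in 20% of 24-month passes and 10% of 36-month passes, so disagreement between them does not identify missed doses.

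Two parts of this stand. The assurance claims more than subset testing can deliver, and four terms are undefined: at-risk, serologic evidence, visit and cutoff.

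The rest depends on reading the at-risk group as something other than the group the protocol has just named. The Analysis section raises unreported doses in girls enrolled at 9-10 and, within the same paragraph, directs HPV6/11 testing to those at risk. An analyst would start with those girls, perhaps narrowed by school grade or birth cohort, since the national programme targets fourth grade. The serologic trigger also need not be a single-visit rule. The girls give blood at 1, 12, 24 and 36 months, and the background data show one-dose HPV-16 GMTs steady from 12 to 48 months (114, 124, 135, 137), so a rise between visits would be visible.

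**Conclusion.** No change is needed. On its natural reading the plan already tests the right girls, and SO3 repeats the analysis without them at the 65% and 84% power for which the trial was sized. SO3 is free of this bias in the age group the protocol names. The operative text is the ATP criterion, which openly limits serology to tested participants. The assurance in SAP section 8 is a loose statement of purpose, and rewording it would alter no result. The missing definitions are details that analysts can fix sensibly before analysis.

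At 2% of girls missed, the false-declaration rate moves from 0.022 to about 0.024 to 0.026 with one plausible trigger. The higher range of 0.030 to 0.049 needs nobody caught and one type exactly at the margin with the other clear. Its top also needs a boost taken from three versus one dose of Cervarix, whereas the outside doses are one or two of Gardasil.

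The missed fraction, the boost, the correlations and the trigger are assumptions. The conclusion also rests on the at-risk group covering essentially all 9-10s who could have been reached by the national programme.
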